1.2 How will you define serious adverse events?

_X_A serious adverse event will be considered any undesirable sign, symptom, or medical condition which is fatal, is life-threatening, requires or prolongs inpatient hospitalization, results in persistent or significant disability/incapacity, constitutes a congenital anomaly or birth defect, is medically significant and which the investigator regards as serious based on appropriate medical judgment. An important medical event is any AE that may not result in death, be life-threatening, or require hospitalization but may be considered an SAE when, based upon appropriate medical judgment, it may jeopardize the patient and may require medical or surgical intervention to prevent one of the outcomes listed in the definitions of SAEs.

__X__Any serious psychological and emotional distress resulting from study participation (suggesting need for professional counseling or intervention).

1.3 What is the definition of an unanticipated problem?

Do not change this answer

An unanticipated problem is any event, experience that meets ALL 3 criteria below:

- Is unexpected in terms of nature, severity or frequency given the research procedures that are described in the protocol-related documents AND in the characteristics of the subject population being studies
- Related or possibly related to participation in research. This means that there is a reasonable
 possibility that the incident may have been caused by the procedures involved in the research
 study.
- The incident suggests that the research placed the subject or others at greater risk of harm than was previously known or recognized OR results in actual harm to the subject or others

1.4 What is the definition of a protocol violation?

Do not change this answer

A protocol violation is defined as any change, deviation, or departure from the study design or procedures of a research project that is NOT approved by the IRB-HSR prior to its initiation or implementation, OR deviation from standard operating procedures, Good Clinical Practices (GCPs), federal, state or local regulations. Protocol violations may or may not be under the control of the study team or UVa staff. These protocol violations may be major or minor violations.

Additional Information: see the IRB-HSR website at http://www.virginia.edu/vpr/irb/HSR_docs/Forms/Protocol_Violations_%20Enrollment_Exceptions Instructions.doc

1.5 If pregnancy occurs how will this information be managed?

_X__ Other – Subjects are counseled to take measures to avoid pregnancy during the study, and the likelihood of pregnancy will not be altered by these study procedures. Pregnancy cannot be considered an adverse event or unanticipated problem related to any of the study procedures. Pregnancy would be considered a protocol violation (on the part of the study volunteer).

1.6 What is the definition of a Protocol Enrollment Exception?

Page 11 of 35

__X_NA- No outside sponsor

1.7 What is the definition of a data breach?

Do not change this answer

A data breach is defined in the HITECH Act (43 USC 17932) as an unauthorized acquisition, access, or use of protected health information (PHI) that compromises the security or privacy of such information.

Additional Information may be found on the IRB-HSR Website: Data Breach

2. Identified risks and plans to minimize risk

2.1 What risks are expected due to the intervention in this protocol?

Expected Risks related to study participation.	Frequency
Risks of venipuncture	
Discomfort	X Occurs frequently
	Occurs infrequently
	Occurs rarely
	Frequency unknown
Bruising	_XOccurs frequently
	Occurs infrequently
	Occurs rarely
	Frequency unknown
Infection	Occurs frequently
	Occurs infrequently
	Occurs rarely
	X_Frequency unknown, but likely to be
	very rare
Blood clot at the site of intravenous	Occurs frequently
catheter insertion	Occurs infrequently
	_XOccurs rarely
	Frequency unknown
Risks of frequent blood draws	
Mild anemia	Occurs frequently
	Occurs infrequently
	Occurs rarely
	X_Frequency unknown
Risk to fetus	Occurs frequently
	Occurs infrequently
	Occurs rarely
	X_Frequency unknown – Extremely
	unlikely, as endogenous progesterone
	concentrations are normally very high during
	pregnancy, and we are administering one

Page 12 of 35

	small dose of progesterone.
Risks of progesterone	
Fluid retention	Occurs frequently
	Occurs infrequently
	Occurs rarely
	X_Frequency unknown - Can occur with
	long-term, higher dose progestin
	administration, but very unlikely to occur after
Classinasa	one small dose of progesterone.
Sleepiness	Occurs frequently
	Occurs infrequently
	Occurs rarely -
	X_Frequency unknown - Unlikely to occur
Mood swings	after one small dose of progesterone. Occurs frequently
Wood Swings	Occurs infrequently
	Occurs rarely
	X Frequency unknown - Can occur with
	long-term, higher dose progestin
	administration, but very unlikely to occur after
	one small dose of progesterone.
Mild vaginal bleeding	Occurs frequently
	Occurs infrequently
	Occurs rarely
	X_Frequency unknown - often occurs after
	longer-term, higher dose progestin
	administration, but very unlikely to occur after
Diaka of iron complementation	one small dose of progesterone.
Risks of iron supplementation	O
nausea	Occurs frequently
	X_Occurs infrequently
	Occurs rarely Fraguency unknown
constipation	Frequency unknown Occurs frequently
σοιτοιιματίστη	X Occurs infrequently
	Occurs rarely
	Frequency unknown
dark stool	X Occurs frequently
dan otoo	Occurs infrequently
	Occurs rarely
	Frequency unknown
Risk for early termination of	Subjects are not expected to have any
study participation if subject	alteration of fertility as a result of study
becomes pregnant	medications. Therefore, sexually active
	subjects may get pregnant during this
	protocol. If the volunteer becomes pregnant,
	the study and all study medications will be
	discontinued.

Page 13 of 35 Version Date: 09/24/14

Violation of subject's privacy and	Minimized due to the requirements of the
confidentiality	privacy plan in this protocol

- 2.2 List by bullet format a summary of safety tests/procedures/observations to be performed.
- Risks of venipuncture will be minimized by using proper sterile technique
- Risk of anemia will be reduced in the following manner: Most importantly, blood withdrawal will be carefully limited to < 550 cc over an 8 week period of time. Specifically, 16 cc will be withdrawn during screening visit, and approximately 155 cc will be withdrawn during each CRU admission (this includes up to 0.5 cc of blood wastage per blood draw). Thus, overall blood withdrawal for the entire protocol will be approximately 325 cc. Also, hemoglobin and hematocrit will be measured and reviewed within 30 days before each CRU sampling study. Only volunteers with hematocrit ≥ 36% or hemoglobin ≥ 12 will be allowed to proceed with the frequent sampling study.

- A history and physical will be performed at screening. Women with disorder that could be exacerbated by
 mild anemia will be excluded: known or suspected congestive heart failure; known or suspected coronary
 atherosclerosis; asthma requiring systemic intermittent corticosteroids; etc.
- We do not believe that this study poses any risk to a fetus. Nonetheless, risk of fetal exposure to study drugs will be reduced by having a serum pregnancy test obtained and reviewed prior to each overnight sampling study. If the volunteer is pregnant, the study and all study medications will be discontinued.
- A single small dose of progesterone is not expected to increase the risk of venous thromboembolism or cancer. Nonetheless, we will exclude women with a history of venous thromboembolism or breast/ovarian/endometrial cancer.
- Risk from iron supplementation will be reduced by instructing subjects to take their iron tablets with food and a full glass of water. They will be told to include whole grains and fruits and vegetables in their diet for fiber.
- A comprehensive metabolic panel will be performed at screening. Women with liver enzymes, alkaline phosphatase, or bilirubin > 1.5 times upper limit of normal (confirmed on repeat) will be excluded, with the exception that mild bilirubin elevations will be accepted in the setting of known Gilbert's syndrome. Women with abnormal renal function (i.e., serum creatinine > 1.4) will be excluded. Women with abnormal sodium, potassium, or bicarbonate concentrations (confirmed on repeat) will be excluded.
- If three months have elapsed between (a) the subject's most recent safety labs and (b) an overnight admission, a CBC, chemistry and liver panel will be obtained prior to the overnight admission (or on admission) to exclude anemia and any other exclusion criteria.
- Subjects will have frequent (at least every 10 minutes) contact with CRU nursing personnel and will be asked to report any unusual symptoms occurring during the protocol.

2.3 Under what criteria would an INDIVIDUAL SUBJECT'S study treatment or study participation be stopped or modified

X_At subject, PI or sponsor's request

Protocol-determined criteria for study withdrawal include pregnancy and persistent anemia despite iron supplementation. The PI could also withdraw a subject if it is felt that continuation would be unsafe. The subject may withdraw at any time and for any (stated or unstated) reason.

__X__Treatment would be stopped if the subject had a serious adverse event deemed related to study, or study drug will be increased if the subject tolerates dosing *insert details*:

Specifically, treatment would be stopped if the subject had a serious adverse event deemed related to study.

Page 14 of 35

	,	ı	,
+	L		L
7	1	t	

2.4 Under what criteria would THE ENTIRE STUDY need to be stopped. These are called stopping rules for early termination of the entire study. *List criteria regardless of whether the study is sponsored or not.* Be sure to include any criteria for which the UVa PI would halt the study at UVa. X Per IRB, PI, DSMB, or sponsor discretion 2.5 What are the criteria for breaking the blind/mask? **X** Other: *specify* The treatment allocation would be unblinded if a serious adverse event occurs during study. Given that progesterone concentrations are measured, treatment allocation will be effectively unblinded once a participant completes study and blood samples are analyzed. 2.6 How will subject withdrawals/dropouts be reported to the IRB prior to study completion? **X** IRB-HSR continuation status form 3. Adverse Event / Unanticipated Problem Recording and Reporting 3.1 Will all adverse events, as defined in section 1.1, be collected/recorded? No ► IF NO, what criteria will be used? X Only adverse events deemed related/possibly related to study 3.2 How will adverse event data be collected/recorded? Check all that apply **X** Paper AE forms/source documents **X** Spreadsheet (paper or electronic) **3.3.** How will AEs be classified/graded? Check all that apply **X** Mild/Moderate/Severe X Serious/Not serious Required for all protocols 3.4 What scale will the PI use when evaluating the relatedness of adverse events to the study participation? **X** The PI will determine the relationship of adverse events to the study using the following scale: Related: AE is clearly related to the intervention Possibly related: AE may be related to the intervention AE is clearly not related to intervention Unrelated:

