 - _X_An adverse event will be considered any undesirable sign, symptom or medical or psychological condition **even if the event is not considered to be related** to the investigational drug/device/intervention. Medical condition/diseases present before starting the investigational drug/intervention will be considered adverse events only if they worsen after starting study treatment/intervention. An adverse event is also any undesirable and unintended effect of research occurring in human subjects as a result of the collection of identifiable private information under the research. Adverse events also include any problems associated with the use of an investigational device that adversely affects the rights, safety or welfare of subjects.

Page 10 of 35

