3.6 When will the recording/reporting of adverse events/unanticipated problems end?

X End of study drug/device/intervention/participation

3.7 How will Adverse Events, Unanticipated Problems, Protocol Violations and Data Breaches be reported? Complete the table below to answer this question

Type of Event	To whom will it be reported:	Time Frame for Reporting	How reported?
Any internal event resulting in death that is deemed DEFINITELY related to (caused by) study participation An internal event is one that occurs in a subject enrolled in a UVa protocol	IRB-HSR	Within 24 hours	IRB Online and phone call www.irb.virginia.edu/
Internal, Serious, Unexpected adverse event	IRB-HSR	Within 7 calendar days from the time the study team received knowledge of the event. Timeline includes submission of signed hardcopy of AE form.	IRB Online www.irb.virginia.edu/
Unanticipated Problems that are not adverse events or protocol violations This would include a Data Breach.	IRB-HSR	Within 7 calendar days from the time the study team received knowledge of the event.	Unanticipated Problem report form. http://www.virginia.edu/vp rgs/irb/HSR_docs/Forms/R eporting_Requirements- Unanticipated_Problems.d oc)
Protocol Violations (The IRB-HSR only requires that MAJOR violation be reported, unless otherwise required by your sponsor, if applicable.) Or	IRB-HSR	Within 7 calendar days from the time the study team received knowledge of the event.	Protocol Violation and Enrollment Exception Reporting Form http://www.virginia.edu/vp rgs/irb/hsr_forms.html
Enrollment Exceptions			Go to 3 rd bullet from the bottom.

Page 16 of 35

Data Breach	The UVa Corporate Compliance and Privacy Office, a	As soon as possible and no later than 24 hours from the time the incident is identified.	UVa Corporate Compliance and Privacy Office- [contact]
	ITC: if breach involves electronic data-	As soon as possible and no later than 24 hours from the time the incident is identified. IMMEDIATELY.	ITC: Information Security Incident Reporting procedure, http://www.itc.virginia.edu/secur ity/reporting.html
	UVa Police if breach includes such things as stolen computers.		Phone- [contact]

	UVa l	PI HELD IND	
Life-threatening and/or fatal unexpected events related or possibly related to the use of the investigational agent.		Within 7 calendar days of the study team learning of the event	Form FDA 3500A (MedWatch) or narrative

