Serious, unexpected and related or possibly related adverse events	FDA	Within 15 calendar days after the study team receives knowledge of the event	Form FDA 3500A (MedWatch) or narrative
All adverse events	FDA	Annually	IND annual report

4.	How will the endpoint data be collected/recorded.	
	X_	_Source documents
	X_	_Database: specify

5. Data and Safety Oversight Responsibility

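### Section 3.1 records only related or possibly related adverse events, so the record cannot supply the annual FDA row of 3.7, as worded, for events rated unrelated

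*Combined protocol and SAP*

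**What the plan says.** All of the relevant text is in the Data and Safety Monitoring Plan of the combined protocol and SAP.

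- Section 1.1 defines an adverse event broadly. An undesirable sign, symptom or condition counts "even if the event is not considered to be related".
- Section 3.1 asks whether all events so defined will be recorded. The answer is no, and the criterion chosen is "Only adverse events deemed related/possibly related to study".
- Section 3.2 names paper AE forms or source documents and a spreadsheet as the recording tools.
- Section 3.4 has the PI rate each event as related, possibly related or unrelated. The last category is for events that are clearly not related.
- Section 3.7 sets out who is told of what. To the IRB-HSR, within 7 calendar days of the team's knowledge, goes an "Internal, Serious, Unexpected adverse event", with the note "Timeline includes submission of signed hardcopy of AE form". In the block for the PI-held IND, the last row sends "All adverse events" to the FDA annually in the IND annual report.

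**The concern.** Section 3.1 decides what enters the record, and 3.7 decides what leaves it as a report. If the reports are worded more widely than the record, staff who follow 3.1 exactly will lack entries that 3.7 asks for.

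What would be at stake is the completeness of the annual safety report, and the chance for someone else to look again at a rating of unrelated. Under 3.1 the investigator's judgement of relatedness alone decides whether an event is kept. The plan does not say what trace, if any, remains of an event left out. A full record has some value here, because item 13b of the pharmacy appendix says that no safety data have been published for this particular suspension. The same item adds that the group has used it in numerous protocols.

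**Working it through.** No figure in the plan has to be reproduced. The check is a comparison of wording, row by row.

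**Adverse-event rows in 3.7**

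| | Row | Recipient or block, timing | Relatedness limit in the row |
|---|---|---|---|
| 1 | "Any internal event resulting in death that is deemed DEFINITELY related to (caused by) study participation" | IRB-HSR, 24 hours | Yes |
| 2 | "Internal, Serious, Unexpected adverse event" | IRB-HSR, 7 calendar days | None |
| 3 | "Life-threatening and/or fatal unexpected events related or possibly related to the use of the investigational agent" | PI-held IND block, 7 calendar days | Yes |
| 4 | "Serious, unexpected and related or possibly related adverse events" | FDA, 15 calendar days | Yes |
| 5 | "All adverse events" | FDA, annually | None |

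The count is 2 IRB-HSR rows + 3 IND rows = 5. Rows with a limit: 1 + 2 = 3. Rows without: 1 + 1 = 2. The rows for unanticipated problems that are not adverse events, for protocol violations and enrollment exceptions, and for data breaches are not counted.

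**What happens to an event rated unrelated**

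| Event rated unrelated | Recorded under 3.1? | Falls in row 2? | Falls in row 5? |
|---|---|---|---|
| Not serious | No | No | Yes |
| Serious, expected | No | No | Yes |
| Serious, unexpected | No | Yes | Yes |

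Row 5, as worded, takes in all three kinds of event, and 3.1 records none of them. Row 2 takes in only the third.

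**Can the two rows be met while 3.1 is followed?**

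- Row 5: not as worded. It is a yearly compilation, and no readable passage names a source for it other than the record that 3.1 governs.
- Row 2: yes. Its clock runs from the team's knowledge of the event and not from an entry in a log, and the row itself calls for a signed AE form. Meeting the row creates the document. What remains is that 3.1 and row 2 do not state the same scope.

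**Can the limit be taken as implied in row 5?** Rows 3 and 4, immediately before it in the same block, both write the limit out. Its absence from row 5 cannot safely be read as an omission of something understood.

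**The case against.** The strongest reply is that 3.1 governs collection and 3.7 governs routing. On that view row 5 means all recorded events, whatever their severity, after two rows confined to grave or serious unexpected ones. This reading is possible. But the two preceding rows restrict both seriousness and relatedness, and row 5 drops both restrictions without saying that one of them survives. No readable passage supplies the narrower meaning, so the mismatch in wording stands, with that ambiguity acknowledged.

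A reader might also infer several stronger points. The documents do not support them.

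- *That 3.1 contradicts 1.1.* It does not. Section 3.1 refers to the 1.1 definition, says openly that not all such events will be recorded, and gives the criterion. That is a declared departure which the form allows for. The mismatch is between 3.1 and 3.7.
- *That the IRB-HSR row cannot be met, or that no form exists for it.* The row runs from knowledge of the event and brings its own form, and nothing in 3.1 forbids completing it. Serious events should reach the team in any case, because 2.5 breaks the blind for a serious adverse event without regard to relatedness.
- *That an FDA requirement is breached.* The documents do not settle what the annual report must contain, and they show no report that was missed.
- *That the filter biases the comparison of progesterone with placebo.* The study is double-blind until data analysis, so relatedness is largely judged blind. The exceptions are serious events, which trigger unblinding, and any judgement made after progesterone results are known. The filter has little scope to favour one arm.

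It is also fair to say that the setting is small and closely watched. Each subject has one 100 mg progesterone dose and one placebo dose. During admissions nurses see subjects at least every 10 minutes, and subjects are asked to report unusual symptoms. This limits the consequence but does not make the two sections agree.

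**Conclusion.** The point holds as a minor inconsistency that should be corrected. Section 3.1 followed exactly leaves the annual FDA row incomplete, as that row is worded, for every event rated unrelated. The IRB-HSR row for serious, unexpected events can be met but does not match the 3.1 filter.

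On size: 2 of the 5 adverse-event rows lack a relatedness limit, and the 3.1 rule applies to at most 36 enrolled subjects, with 12 completers sought. That row count describes the wording and does not measure harm. The documents give no rate of unrelated events, so the number that would be left out cannot be estimated. Only events judged clearly unrelated are affected. The primary LH pulse-frequency analysis is unaffected.

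The conclusion assumes that row 5 means what it says, and that the record under 3.1 is its source. If the plan meant recorded events only, the defect is one of unclear wording. Confidence is medium for that reason. The list of items for DSMB review is damaged in the text available and plays no part in this conclusion.

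**What to change.** Change the answer in 3.1 so that all adverse events as defined in 1.1 are recorded, each with the PI's rating on the existing 3.4 scale of related, possibly related or unrelated. Relatedness then becomes an attribute of a recorded event and no longer a condition of entry, and 3.1 agrees with both unlimited rows of 3.7.

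Do not reach agreement the other way, by narrowing those two rows to related or possibly related events. Nothing in the documents shows that the study team may narrow what goes to the IRB-HSR or the FDA. Doing so would also remove reports of serious, unexpected events judged unrelated, which reduces oversight.

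The cost is one wording change in 3.1 and a few more lines on the existing AE forms and spreadsheet, for at most 36 subjects. No new visit, assessment or rating scale is needed.

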3.5 When will recording/reporting of adverse events/unanticipated problems begin?

Page 15 of 35

__X__After subject begins study drug/ device placement/intervention /study-related procedure/specimen collection

3.6 When will the recording/reporting of adverse events/unanticipated problems end?

X End of study drug/device/intervention/participation

3.7 How will Adverse Events, Unanticipated Problems, Protocol Violations and Data Breaches be reported? Complete the table below to answer this question

Type of Event	To whom will it be reported:	Time Frame for Reporting	How reported?
Any internal event resulting in death that is deemed DEFINITELY related to (caused by) study participation An internal event is one that occurs in a subject enrolled in a UVa protocol	IRB-HSR	Within 24 hours	IRB Online and phone call www.irb.virginia.edu/
Internal, Serious, Unexpected adverse event	IRB-HSR	Within 7 calendar days from the time the study team received knowledge of the event. Timeline includes submission of signed hardcopy of AE form.	IRB Online www.irb.virginia.edu/
Unanticipated Problems that are not adverse events or protocol violations This would include a Data Breach.	IRB-HSR	Within 7 calendar days from the time the study team received knowledge of the event.	Unanticipated Problem report form. http://www.virginia.edu/vp rgs/irb/HSR_docs/Forms/R eporting_Requirements- Unanticipated_Problems.d oc)
Protocol Violations (The IRB-HSR only requires that MAJOR violation be reported, unless otherwise required by your sponsor, if applicable.) Or	IRB-HSR	Within 7 calendar days from the time the study team received knowledge of the event.	Protocol Violation and Enrollment Exception Reporting Form http://www.virginia.edu/vp rgs/irb/hsr_forms.html
Enrollment Exceptions			Go to 3 rd bullet from the bottom.

Page 16 of 35

Data Breach	The UVa Corporate Compliance and Privacy Office, a	As soon as possible and no later than 24 hours from the time the incident is identified.	UVa Corporate Compliance and Privacy Office- [contact]
	ITC: if breach involves electronic data-	As soon as possible and no later than 24 hours from the time the incident is identified. IMMEDIATELY.	ITC: Information Security Incident Reporting procedure, http://www.itc.virginia.edu/secur ity/reporting.html
	UVa Police if breach includes such things as stolen computers.		Phone- [contact]

	UVa l	PI HELD IND	
Life-threatening and/or fatal unexpected events related or possibly related to the use of the investigational agent.		Within 7 calendar days of the study team learning of the event	Form FDA 3500A (MedWatch) or narrative
Serious, unexpected and related or possibly related adverse events	FDA	Within 15 calendar days after the study team receives knowledge of the event	Form FDA 3500A (MedWatch) or narrative
All adverse events	FDA	Annually	IND annual report

4.	How will the endpoint data be collected/recorded.	
	X_	_Source documents
	X_	_Database: specify

5. Data and Safety Oversight Responsibility

